#### 4.3.9. Time to First Response of TIS20, TIS40, and TIS60

Time to first response of TIS20, TIS40, and TIS60 is defined as the time between randomization date and the date of the first response (response as defined in Section 4.3.7, Section 4.2.2, and Section 4.3.8, respectively).

Participants without a TIS response will be censored as follows:

- If the participant had a relevant IE, then the censor date will be the last scheduled TIS assessment prior to the relevant IE.
- If the participant did not have a relevant IE, then the censor date will be the last scheduled TIS assessment. If there are no postbaseline TIS values, then the censor date will be the date of randomization.

Time to first response = date of response/censor date - randomization + 1

The distribution of time to response will be estimated using Kaplan-Meier method and compared between the treatment arms during the RCP. A log-rank test will be generated to test for differences in the distribution of time to first TIS response by arms. A Cox-proportional regression model with treatment intervention will be performed. The hazard ratio and corresponding 80% CIs and p-value will be presented.

Kaplan-Meier plots of time to first response of TIS20, TIS40, and TIS60 will also be generated.

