#### **Primary Estimand**

The estimand is described by the following attributes:

- Population: Adult dermatomyositis (DM) participants who have an inadequate response or are intolerant to at least 1 DM treatment
- Endpoint: TIS40 response at Week 26
- Treatment: Ravulizumab versus Placebo
- Intercurrent events (IEs): Receipt of acute therapy with standard DM treatment or prohibited medications, and discontinuation of study intervention due to an AE or lack of efficacy or death during the RCP
  - Such IEs will be addressed via a composite strategy, where participants will be assumed to be TIS40 nonresponders (regardless of the observed TIS value) at all timepoints after first occurrence of either (1) receipt of acute therapy with standard DM treatment and/or prohibited medication, or (2) discontinuation of study intervention due to an AE or lack of efficacy or death
- Population-level summary: Difference in the percentage of TIS40 response between the ravulizumab and placebo arms

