#### 4.1.3. Handling of Dropouts or Missing Data

No imputation will be performed for missing baseline values. For postbaseline data, any imputation will be specified in the derivation of the endpoint.

Missing outcome data due to the coronavirus disease 2019 (COVID-19) pandemic (eg, dropout due to COVID-19) is assumed missing-at-random.

Missing data for quality of life (QoL) instruments will be handled as specified in Section 6.3.

The following relevant IEs may occur during the study:

- Receipt of acute therapy with standard DM treatment therapy or prohibited medications
- Treatment discontinuation due to AE, lack of efficacy, or death

The handling of these relevant IEs is detailed in each analysis section.

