Participants will be defined as a responder at Week 26 if:

- 1. The participant response is almost clear or clear at Week 26 and
- 2. The participant did not have a relevant IE (defined in Section 4.2 and Table 2) up to and including Week 26 and
- 3. The participant demonstrated an improvement from Baseline (eg, mild at baseline to almost clear at Week 26 and almost clear at baseline to clear at Week 26).

Otherwise, the participant will be counted as a non-responder in the randomized treatment arm.

The proportions of participants with a CDA-IGA response (almost clear or clear) at Week 26 in each treatment group along with an exact 2-sided 80% CIs using the Clopper-Pearson method will be presented. The differences in proportions between treatment arms, along with 2-sided 80% CIs using Chan and Zhang method (Chan, 1999), will be presented. Barnard's unconditional exact method will be applied to test whether there is a difference in the proportions between the 2 treatment groups.

The analysis as stated above will also be performed at earlier scheduled visits (Weeks 2, 10, and 18), but statistical testing will not be conducted.

## 4.3.7. TIS20 Response at Week 26

A TIS20 response is defined as an IMACS-TIS  $\geq$  20.

Participants will be defined as a responder at Week 26 if:

- 1. The participant achieves  $TIS \ge 20$  at Week 26 and
- 2. The participant did not have a relevant IE up to and including Week 26 (defined in Section 4.2 and Table 2)

Otherwise, the participant will be counted as a nonresponder at Week 26 in the randomized treatment arm.

The analysis method as stated in Section 4.2.2 will be used to assess TIS20 at Week 26.

#### 4.3.8. TIS60 Response at Week 26

A TIS60 response is defined as an IMACS-TIS  $\geq$  60.

Participants will be defined as a responder at Week 26 if:

- 1. The participant achieves  $TIS \ge 60$  at Week 26 and
- 2. The participant did not have a relevant IE up to and including Week 26 (defined in Section 4.2 and Table 2)

Otherwise, the participant will be counted as a nonresponder at Week 26 in the randomized treatment arm.

The analysis method as stated in Section 4.2.2 will be used to assess TIS60 at Week 26.

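### SAP 4.3.9 censors participants at an intercurrent event after which its own response definition rules out response, so the Kaplan-Meier time-to-response curves run too high

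*SAP*

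**What the plan says.** SAP Section 4.3.9 defines three time-to-event endpoints and takes the event from the binary endpoints: "response as defined in Section 4.3.7, Section 4.2.2, and Section 4.3.8, respectively". Among participants with no response, those with a relevant intercurrent event (IE) fall under this rule: "If the participant had a relevant IE, then the censor date will be the last scheduled TIS assessment prior to the relevant IE". For the rest: "If the participant did not have a relevant IE, then the censor date will be the last scheduled TIS assessment". The estimator is stated as: "The distribution of time to response will be estimated using Kaplan-Meier method and compared between the treatment arms during the RCP", with a log-rank test, a Cox hazard ratio and Kaplan-Meier plots. No competing-event or non-responder version is planned.

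SAP Section 4.1.3 lists the relevant IEs. One is acute therapy or prohibited medication. The other is "Treatment discontinuation due to AE, lack of efficacy, or death".

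The cited Sections 4.2.2, 4.3.7 and 4.3.8 each require that no relevant IE has occurred. Sections 4.3.7 and 4.3.8 then close with: "Otherwise, the participant will be counted as a nonresponder at Week 26 in the randomized treatment arm". Section 4.2.2 has the same rule and repeats the analysis at Weeks 2, 10 and 18.

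**The concern.** Kaplan-Meier reads as a response probability only if censored participants would have gone on to respond at the same rate as those still at risk. Here they cannot. By the definition Section 4.3.9 adopts, a participant with an IE before any response is a non-responder from then on. Stopping for lack of efficacy, and acute therapy given after Clinical Worsening, also depend on how the participant is doing, so the censoring is informative.

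At stake are the displayed curves and their Week 26 values. They would overstate how many participants respond, by an amount that depends on each arm's IE pattern. They would also differ from the by-visit TIS20, TIS40 and TIS60 proportions for a reason that comes only from the censor date.

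**Working it through.** **Inputs.** Section 4.3.9 states no figure of its own. SAP Section 5 gives 36 participants randomized 2:1 (24 and 12), a placebo TIS40 rate of 23% and a 45-point difference, hence 68% on ravulizumab. Its power of about 80% is reproduced if the 20% dropouts count as non-responders. The rates are then 0.8 × 23% = 18.4% and 0.8 × 68% = 54.4%, and the pooled two-sample z test at two-sided 0.20 with 24 and 12 has 81.6% power. Counting only 28.8 evaluable participants gives 87%. Nothing below depends on which reading was meant.

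**Assumptions (not in the documents).** True cumulative first response before any IE is R = 23% or 68%. It is split 5/30/35/30% over Weeks 2, 10, 18 and 26. A share q of each arm has an IE and no prior response. In the main cases half of these fall between Weeks 10 and 18 and half between Weeks 18 and 26, because Protocol Section 6.5.3 advises against acute therapy in the first 10 weeks.

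**Formula.** At each visit, Kaplan-Meier multiplies S by 1 − (new responders ÷ still at risk). Under the SAP rule, participants with an IE since the previous visit have already left the risk set. If they stay in as non-responders, 1 − S at Week 26 equals R exactly.

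**Placebo, q = 40%**
- Week 2: S = 1 − 0.0115 = 0.9885
- Week 10: S = 0.9885 − 0.0690 = 0.9195
- Week 18: at risk 0.9195 − 0.20 = 0.7195; S = 0.9195 × (1 − 0.0805/0.7195) = 0.8166
- Week 26: at risk 0.7195 − 0.0805 − 0.20 = 0.4390; S = 0.8166 × (1 − 0.0690/0.4390) = 0.6883
- Kaplan-Meier response 31.2%, against a true 23%

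**Ravulizumab, q = 10%**
- Week 10: S = 1 − 0.034 − 0.204 = 0.762
- Week 18: S = 0.762 × (1 − 0.238/0.712) = 0.5073
- Week 26: S = 0.5073 × (1 − 0.204/0.424) = 0.2632
- Kaplan-Meier response 73.7%, against a true 68%

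**Range** (differences taken before rounding; the true difference is 45 points)

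| IE share, placebo / ravulizumab | Placebo (true 23%) | Ravulizumab (true 68%) | Difference |
|---|---|---|---|
| 10% / 10% | 24.4 (+1.4) | 73.7 (+5.7) | 49.3 |
| 20% / 10% | 26.0 (+3.0) | 73.7 (+5.7) | 47.6 |
| 40% / 10% | 31.2 (+8.2) | 73.7 (+5.7) | 42.5 |
| 40% / 20% | 31.2 (+8.2) | 81.9 (+13.9) | 50.8 |
| 40% / 0% | 31.2 (+8.2) | 68.0 (0) | 36.8 |
| 40% / 10%, all IEs between Weeks 2 and 10 | 37.9 (+14.9) | 75.5 (+7.5) | 37.6 |

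Harsher assumptions exceed this range. With all IEs between Weeks 2 and 10, 20% on ravulizumab gives +16.9 and 50% on placebo gives +22.4.

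**Second set of assumptions.** Take placebo response hazards of 0.02, 0.08, 0.10 and 0.10 at the four visits. Kaplan-Meier is 1 − 0.98 × 0.92 × 0.90 × 0.90 = 27.0%. Cumulative incidence is 24.3%, 21.9% or 19.4% when 14%, 27% or 39% have an IE. For ravulizumab, hazards of 0.05, 0.25, 0.30 and 0.30 give 65.1%, against 61.3% when 7.5% have an IE. The difference between arms is 38.1 points by Kaplan-Meier, against 37.0, 39.4 or 41.9.

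**Hazard ratio.** In a simulation with 24 and 12 participants, under the first set of assumptions, the hazard ratio fell from about 3.6 to 3.1 at 40%/10%. It barely differed between the two rules at 20%/10% (3.64 and 3.61) and at 40%/20% (3.66 and 3.59).

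**The case against.** Four points on the other side carry weight.

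- **Cause-specific reading.** Censoring at a competing event gives a cause-specific hazard comparison, a legitimate quantity that does not require failures to go on to respond. This stands for the log-rank test and the Cox model, though the SAP does not label them so. It does not rescue the Kaplan-Meier curves as response probabilities.
- **Some disagreement is inherent.** First response at any visit and response at Week 26 differ anyway, since a participant may respond at Week 10 and later lose response. This stands, and the fix removes only the part due to the censor date.
- **Other displays exist.** Section 4.2.2 already plots by-visit TIS40 proportions with IEs as non-response, and Section 4.3.11 tabulates acute therapy by arm. That helps a careful reader but leaves the time-to-response curves as they are.
- **Low inferential weight.** SAP Section 4.3 plans no formal testing of secondary endpoints, and about 12 participants receive placebo. This limits the importance of the point, not its correctness.

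A reader might also infer that the rule contradicts the primary composite estimand, "where participants will be assumed to be TIS40 nonresponders (regardless of the observed TIS value) at all timepoints after first occurrence of either" an IE. The documents do not support that. That estimand covers TIS40 at Week 26, Protocol Section 3.2 says secondary estimands do not apply to Part A, and SAP Section 4.3 sets IE handling endpoint by endpoint. The inconsistency is with the response definitions that Section 4.3.9 itself cites.

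**Conclusion.** The point holds. Where IEs precede response, the planned Kaplan-Meier curves overstate the probability of response, and no competing-event or non-responder version is planned to correct them. Across the tabulated cases the overstatement is about 1 to 15 points in an arm with such IEs and nil in an arm without them. With IEs after Week 10 the apparent difference runs from 36.8 to 50.8 points against a true 45. These sizes rest on assumed IE rates, IE timing and response timing, and on borrowing 23% and 68% from the sample-size section as cumulative response.

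A reader might infer that the inflation is always largest in the arm with more rescue, so that the treatment effect is understated. That does not follow. At 20% placebo and 10% ravulizumab IEs, ravulizumab rises by 5.7 points and placebo by 3.0. Under the second set of assumptions ravulizumab at 7.5% rises by 3.8, and placebo at 14% by 2.7. A higher later response rate among those still at risk can outweigh a lower IE rate, so the contrast may shrink or widen and the rule cannot be assumed conservative. The documents also do not say which arm will have more IEs.

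**What to change.** In SAP Section 4.3.9, keep participants with a relevant IE and no prior response in the risk set as non-responders, censored at the planned end of the randomized period (Day 183). Protocol Table 1 allows ± 3 days at that visit, so use nominal visit days, or a censor day no earlier than the last Week 26 assessment. Otherwise a response dated after Day 183 would find them already removed. Equivalently, show cumulative incidence with the IE as a competing event; the two agree when nobody else is censored early.

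Retain the present censoring as a supplementary analysis, and label its hazard ratio cause-specific.

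The cost is a few lines of SAP text and a changed censor date in one dataset, with no new data or visits. The downside is that the displayed response curves will be somewhat lower. Protocol Table 8 lists the same endpoint for Part B, whose SAP is not among these documents, so the rule is best settled before it is carried over.

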#### 4.3.10. CW During RCP at 2 Consecutive Visits

If a participant meets any of the following criteria on 2 consecutive visits during the RCP, then the participant will be defined as meeting the criteria for CW:

- 1. Physician's global activity visual analog scale (VAS) worsening  $\geq 2$  cm and manual muscle testing subset of 8 muscles (MMT-8) worsening  $\geq 20\%$  compared with Baseline
- 2. Global extramuscular disease activity worsening ≥ 2 cm on the Myositis Disease Activity Assessment Tool VAS compared to Baseline
- 3. Any 3 of 5 CSMs (excluding muscle enzymes) worsening by  $\ge$  30% compared with Baseline

The same criteria need not be met at both visits. A summary of the overall number of participants who met CW by treatment arm will be presented. A separate listing of the participants who met CW along with the criteria will be presented.

An additional analysis that will also include any participant who achieves CW during the RCP at a visit (for instance, including any participant who achieves CW at Week 26 and is unable to confirm the event during the RCP) will be performed.

#### 4.3.11. Receipt of Acute Therapy With Standard DM Treatment

Acute therapy with standard DM treatment therapy may be provided during the RCP if the participant met CW or for other safety reasons. Any participants who receive acute therapy with standard DM treatment medication will need to discontinue study intervention. A summary of the overall number of participants who received acute therapy with standard DM treatment during the RCP will be summarized by treatment arm. A separate listing of the participants who receive acute therapy with standard DM treatment will be presented.

## 4.4. Exploratory Endpoints

All exploratory endpoints will be analyzed using the Randomized Set. These analyses will be descriptive in nature. For these endpoints, if any participant experiences a relevant IE of acute therapy with standard DM treatment/prohibited medication or treatment discontinuation due to AE, lack of efficacy, or death, the data will be set to missing after the IE and there will be no imputation.

#### 4.4.1. Change From Baseline in EQ-5D-5L at Week 26

The European Quality of Life Health 5-item questionnaire dimensions 5-level (EQ-5D-5L) is self-assessed instrument. This instrument consists of 5 domains (mobility, self-care, usual activities, pain/discomfort, and anxiety/depression) and VAS. The VAS ranges from 0 to 100, where lower values represent the worst QoL.

Descriptive statistics of actual and change from Baseline in VAS will be presented by treatment and scheduled visit. For each of the 5 domains, categorical summaries of the percentage of participants reporting ordinal responses (1 to 5) will be presented by treatment and scheduled visit. In addition, an overall shift table of Baseline to worst post-Baseline during the RCP will be generated by treatment arm for each of the 5 domains.

## 4.4.2. Change From Baseline in PROMIS-29 v2.1 Domains at Week 26

The Patient-Reported Outcomes Measurement Instrument System (PROMIS)-29 v2.1 is a QoL instrument used to assess pain intensity on a Likert scale for each of the health domains (physical function, fatigue, pain interference, depressive symptoms, anxiety, ability to participate in social roles and activities, and sleep disturbance) using 4 items per domain. For each of the health domains, a total score will only be calculated if there are no missing items per domain. The total score will be the sum of the responses for each question.

Descriptive statistics of actual and change in total score will be presented by treatment arm and scheduled visit.

## 4.4.3. Change From Baseline in Short Form Health Survey (36 Questions Version) at Week 26

The Short Form Health Survey (36 Questions Version) (SF-36; Version 2.0) is a 36-item self-report of health-related QoL (HR-QoL). It contains 8 subscales measuring different domains of HR-QoL: physical functioning, role limitations due to physical problems, bodily pain, general health perceptions, vitality, social functioning, role limitations due to emotional problems, and mental health. The 2 summary scores are the physical component summary (PCS) and the mental component summary (MCS). There is no single overall score for the SF-36.

Descriptive statistics of actual and change in each of the 8 subscales, as well as the PCS score and MCS score, from Baseline will be generated by treatment arm and scheduled visits.

#### 4.4.4. Change in DM Symptoms Captured in DM-DSQ at Week 26

Analyses of this endpoint will be summarized in a separate SAP.

## 4.4.5. Change From Baseline in Participant Self-Assessment of Disease Activity at Week 26

Analyses of this endpoint will be summarized in a separate SAP.

#### 4.4.6. Exploratory Biomarkers

Exploratory biomarker analyses will be outlined in a separate SAP.

## 4.4.7. Change from Baseline Using Scale to Measure Pruritus (5D-Itch Scale) at Week 26

Descriptive statistics of actual and change from Baseline in total 5D score at each visit will be generated.

## 4.4.8. Incidence of Protocol-Defined CW During RCP

A time-at-risk-adjusted incidence rate will be calculated. This incidence rate is defined as the number of participants who experience CW divided by the total person-years at risk for the event. CW during the RCP will be defined as a participant meeting the criteria as specified in Section 4.3.10 at 2 consecutive visits. The total person-years at risk will be defined differently for participants with and without the event of CW. For participants with an event, the risk is defined as (date of the criteria being met for CW - first dose date + 1)/365.25. If the participant did not experience an event, the risk is defined as (latest visit date of TIS during the RCP - first dose date + 1)/365.25. Total person-years at risk will be the sum of the person-years at risk for all participants in each treatment group. A summary table displaying the total person-years at risk and the number of participants with an event will be displayed.

## 4.4.9. Change From Baseline in Handheld Dynamometry Performance at Week 26

Handheld dynamometry is a procedure for quantitative strength testing. Muscle strength testing will be performed at baseline and Week 26. Derivations are specified in Section 6.1.6.

Descriptive statistics of actual values and change from Baseline will be summarized by visit for the handheld dynamometry (HHD) data.

#### 4.4.10. Change From Baseline in 30-second Chair Stand Test (30s CST) at Week 26

The 30-second Chair Stand Test (30s CST) will count the number of times the participant is able to stand in 30 seconds at baseline and Week 26. Descriptive statistics will be generated.

#### 4.4.11. Change From Baseline in Functional Assessment of Chronic Illness Therapy – Fatigue Scale at Week 26

Descriptive statistics of actual and change from Baseline in Functional Assessment of Chronic Illness Therapy – Fatigue Scale (FACIT-Fatigue) scores at each visit will be generated.

## 4.5. OLE Analysis

Descriptive analyses of key safety and efficacy will be generated based on data collected as of the data cutoff in the OLE Set.

The efficacy analyses may include endpoints such as, but not limited to, the following:

- TIS over time
- TIS response rate for TIS20, TIS40, and TIS60
- Change from Baseline in CDASI

A subset of key safety tables in the OLE Set such as, but not limited to, disposition, baseline disease characteristics, total exposure and adverse events (AEs) may also be summarized. For efficacy and safety summaries of the OLE population, the Baseline will be relative to the first dose of study intervention.

Additionally, similar analyses as noted above may also be conducted using the All Ravulizumab-Treated Set summarizing data across the study periods (RCP and OLE). For these summaries, the Baseline will be relative to the first dose of ravulizumab.

## 4.6. Safety Analyses

The safety and tolerability of ravulizumab will be assessed based on Exposure, Adverse Events, clinical laboratory findings, vital signs findings, electrocardiogram (ECG) abnormalities, and physical examinations. All safety analyses will be performed on the Safety Set (SS) based on the actual treatment received.

#### 4.6.1. Exposure

Summaries of exposure during the RCP will include the following categories such as, but not limited to, total number of infusions received per participant, total dose (mg), cumulative dose drug exposure, number of missed infusions, and number of interrupted infusions.

Treatment duration will be calculated (in weeks) as the difference between the last dose date and the first dose date + 1 divided by 7. This will be summarized as descriptive statistics.

In addition, the total number of participants who missed an infusion and reason will be summarized by treatment group and overall. A by-participant listing of participants with a missed infusion will be generated separately with reason for not done.

#### 4.6.2. Adverse Events

AEs will be classified using the Medical Dictionary for Regulatory Activities (MedDRA Version 26.0 or later) and displayed in tables using System Organ Class (SOC) and Preferred Terms (PT). Treatment-emergent AEs are defined as any AE with a start date on or after the first dose of study intervention in the RCP.

An AE overview table will be tabulated. This table will include the number and percentage of participant in the following categories such as, but not limited to, the following:

- At least 1 treatment-emergent adverse event (TEAE)
- At least 1 drug-related TEAE
- At least 1 TEAE of Grade 3, 4, or 5
- At least 1 serious TEAE
- At least 1 serious related TEAE
- At least 1 adverse event of special interest (AESI)
- At least 1 AE leading to treatment discontinuation
- At least 1 drug-related AE leading to treatment discontinuation
- At least 1 infusion-related reaction

Tabulations by SOC and PT displaying the number of participants (percentage) and total event will be generated for the following tables:

- All TEAEs
- TEAEs of Grade 3, 4, or 5
- AEs related to treatment
- AEs related to treatment by maximum severity
- AESI
- Serious Adverse Events (SAEs)
- SAEs related to treatment
- AEs leading to treatment discontinuation
- Infusion Associated Related Reactions

Separate listings will be provided for deaths, SAEs, and any AEs leading to study withdrawal or treatment discontinuation. In addition, a separate AE listing will be generated for any AE related to COVID-19.

In addition, there will be a separate listing for any pretreatment AEs. These AEs will not be included in the summary tables of TEAEs. Pretreatment AEs are defined as AEs that start after informed consent but before the first dose of study intervention.

